#### Age

The age of a subject is defined as the number of whole calendar years from the subject's date of birth to the date of informed consent.

#### Baseline Value

For purposes of analysis, the baseline value is defined as the last non-missing value obtained prior to initiation of study medication.

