7. STUDY TREATMENT

7.1. Investigational Study Medication

The study medications for this study are ATI-50002 Topical Solution in dosage strengths of 0.46% and 0.12% and Vehicle Topical Solution. The study medications are formulated as thin clear solutions that are indistinguishable as packaged and labelled. The inactive ingredients include: water, transcutol P, propylene glycol, PEG400, dimethyl sulfoxide (DMSO), kolliphor CS 20, benzyl alcohol, poloxamer 188, and povidone K30.

STUDY MEDICATION INFORMATION				
Study medication name	Double-Blind Period			Open-Label Period
	ATI-50002	ATI-50002	Vehicle	ATI-50002
Dosage Strength	0.46%	0.12%	-	0.46%
Manufacturer	PMRS, Inc., Horsham, PA			
Pharmaceutical Form	Topical Solution			
Container	Amber Glass Bottle, 120 mL with screw cap			
Storage Conditions	59°F to 77°F (15°C to 25°C)			
Dose regimen				
Route	Topical			
Frequency	Twice-daily			
Duration of administration	24 weeks		24 Weeks	
Other supplies	Disposable, single-use droppers will be provided.			

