### 3.3.6. Definitions and Terminology

#### Day 1 (DB)

Day 1 (DB) is defined as the date of the initial study medication application as reported on the study medication usage page of the CRF.

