#### Change from Baseline

Change from Baseline for a given endpoint is defined as the value at the analysis visit minus the baseline value.

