#### Adverse Event (AE)

An AE is any untoward medical occurrence in a subject administered a study medication(s) and which does not necessarily have a causal relationship with the study medication. An AE can therefore be any unfavorable and unintended sign or symptom associated with the use of a study medication (including an abnormal laboratory finding), whether related to the study medication. Thus, any new, clinically significant worsening of an existing sign, symptom or disease, should be considered an AE. Every new episode or clinically significant worsening of a chronic condition (*e.g.*, headaches, seasonal allergies, depression, or hypertension) should be reported as a separate AE, even if the condition is reported in the subject's medical history.

Treatment-Emergent Adverse Event (TEAE)

For the interim analysis of the DB treatment period, any recorded AE that occurs on or after the initiation of study medication and within 31 days after the date of Visit 10 or after the date of last DB dose of study medication will be considered treatment-emergent. For the OLE period analysis, an AE that occurs on or after the initiation of OLE study medication and within 31 days after the date of last dose of study medication will be considered treatment-emergent.

Treatment-emergent Laboratory Abnormalities

A treatment-emergent laboratory abnormality is defined as a result in which the baseline value is within normal laboratory limits and the post-baseline value is outside normal laboratory limits. If the relevant baseline assessment is missing, then any post-baseline value outside normal laboratory limits is treatment-emergent.

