### **5.3.4. Open-Label Extension Safety Analyses**

Adverse events, laboratory values, and vital signs will be used in the OLE period to assess safety. Results occurring in just the OLE period will be reported based on the same treatment groups used for reporting during the DB portion of the study. The same analyses planned for the DB period will be generated for the OLE. Additionally, pooled AE displays will be developed. For the pooled analysis, only AEs in the OLE would apply to the patients randomized to vehicle during the DB

portion of the study. For patients randomized to ATI-502 during the DB portion, their complete AE profile for the entire study should be summarized in the pooled analysis.

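### In the open-label safety tables, former-vehicle subjects' laboratory and vital-sign changes are measured from a value taken before vehicle, about 24 weeks or more before their first active dose.

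*SAP*

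**What the plan says.** SAP 3.3.6 has a single baseline definition, not specific to a period: "the baseline value is defined as the last non-missing value obtained prior to initiation of study medication". It then states: "Change from Baseline for a given endpoint is defined as the value at the analysis visit minus the baseline value". Protocol 7.1 makes clear that vehicle falls under that term: "The study medications for this study are ATI-50002 Topical Solution in dosage strengths of 0.46% and 0.12% and Vehicle Topical Solution".

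For laboratory data, SAP 3.3.6 defines a treatment-emergent abnormality as "a result in which the baseline value is within normal laboratory limits and the post-baseline value is outside normal laboratory limits", and SAP 5.3.2 restates the rule. Neither place gives an OLE version.

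SAP 5.3.4 covers safety in the OLE: "The same analyses planned for the DB period will be generated for the OLE". Results are to be grouped by double-blind treatment assignment. SAP 8.2 lists OLE tables of change from baseline for hematology, chemistry and vital signs (items 29, 31, 35) and of treatment-emergent abnormal hematology, chemistry and urinalysis (items 30, 32, 34). Under Protocol 7.2 everyone in the OLE receives 0.46%.

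Elsewhere the SAP does move the anchor. An OLE treatment-emergent adverse event is "an AE that occurs on or after the initiation of OLE study medication" and within a set time after the last dose. The pooled adverse event displays in SAP 5.3.4 count only OLE events for subjects randomised to vehicle. SAP 5.2.9 shows OLE efficacy both from study day 1 and from Visit 10.

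**The concern.** For a subject randomised to vehicle, the OLE is the first exposure to ATI-50002. A reader of the OLE laboratory tables will take an emergent abnormality there to be one that appeared after 0.46% was started, and a change from baseline to be change on 0.46%. With a reference taken before vehicle, neither holds.

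Two errors follow, in opposite directions. Abnormalities already present when the OLE began are counted as emerging in it. Some that do begin on 0.46% are left out because the analyte was also abnormal at Day 1, months earlier. Mean changes, including those for vital signs, add drift over the vehicle period to any on-drug change. Long-term safety of 0.46% is a stated objective (Protocol 4.4), and these tables are part of the evidence for it.

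The plan is also uneven. A raised enzyme that arose on vehicle and persisted is not an OLE treatment-emergent adverse event, yet the same raised value is treatment-emergent in the OLE laboratory table.

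**Working it through.** **Which baseline applies in the OLE**

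1. Baseline precedes initiation of study medication (SAP 3.3.6). Vehicle is study medication (Protocol 7.1), so for vehicle subjects initiation is the first vehicle application.
2. "Day 1 (DB) is defined as the date of the initial study medication application" (SAP 3.3.6). Study Day is counted from that date. SAP 5.2.9 glosses baseline in the OLE as study day 1, which is the double-blind Day 1.
3. SAP 5.3.4 carries the double-blind analyses over with no replacement. Read as written, the OLE laboratory and vital-sign tables use the pre-vehicle value.

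**How old that value is at the first 0.46% application**

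Inputs are the visit days in the protocol schedule (Section 6.3). Week 24 is Day 24 × 7 + 1 = 169 and Week 28 is Day 28 × 7 + 1 = 197; both match the schedule. With baseline taken on Day 1:

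- Entry at Visit 10: 169 − 1 = 168 days. With the ±3-day window, 165 to 171 days.
- Entry at Visit 11 on its target day: 197 − 1 = 196 days.
- Entry 30 days after a Visit 11 held 3 days late: 196 + 3 + 30 = 229 days. Later entry is allowed, with no stated upper limit.

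For entry at Visit 10, the first OLE laboratory visit (OLE Day 15) is compared with a value 168 + 14 = 182 days old. Only 14 of those days are on active drug (14/182 = 7.7%). At OLE Day 169 the span is 168 + 168 = 336 days, half of it on vehicle.

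**What is counted, by pattern** (Day 1; last value before the OLE; OLE visit)

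- Normal, normal, abnormal: counted with either reference.
- Normal, abnormal, abnormal: counted as written; not counted with a pre-OLE reference.
- Abnormal, normal, abnormal: not counted as written; counted with a pre-OLE reference.
- Abnormal, abnormal, abnormal: counted with neither.

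The two references disagree only in the second and third patterns. An abnormality that arose on vehicle, had returned to normal by the last pre-OLE value and then recurs belongs to the first pattern and is counted either way.

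**How many subjects**

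The documents give neither the number of vehicle subjects entering the OLE nor the rate of vehicle-period abnormalities. Purely as an illustration, let N subjects enter and let a proportion q follow the second pattern on a given test. The expected miscount is N × q:

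- N = 20: 0.4, 1 or 2 subjects for q = 2%, 5% or 10%.
- N = 40 (every planned vehicle subject): 0.8, 2 or 4 subjects.

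**Whether a better value exists**

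Laboratory tests and vital signs are scheduled at Visits 10 and 11, and at OLE Visit 1 when entry is more than 30 days after Week 28. With these, the 168- or 196-day distance becomes about zero for entry at Visit 10 or Visit 11. For entry within 30 days after Visit 11, no laboratory sample is scheduled at OLE Visit 1, so the laboratory reference could be up to 30 days old.

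**The case against.** The best counter-argument is that the SAP is silent on the OLE safety baseline, not wrong about it. The Day 1 baseline window in SAP 3.3.7 sits in a rule introduced for the double-blind period, the SAP defines a separate OLE Day 1 and Period Day, and the missing-baseline rule speaks of the relevant baseline, which could imply more than one. None of this supplies an OLE baseline. Period Day numbers days, the missing-baseline rule defines nothing, and the only gloss on baseline in the OLE (SAP 5.2.9) is study day 1.

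Other parts of the objection stand and limit the point:

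- OLE results are shown by double-blind group, so these subjects sit in a former-vehicle column. The double-blind tables and the subject listings let a reader trace when an abnormality first arose.
- Out-of-range laboratory results and abnormal vital signs judged clinically significant after first treatment must be reported as adverse events (Protocol 8.4.1 and 8.4.3), and those are anchored correctly in the OLE.
- The term treatment-emergent is applied to laboratory values, not to vital signs. For vital signs only the change from baseline is affected.
- Day 1 is the only value free of the formulation's excipients, so it should be kept. Replacing it for one group alone would leave columns of the same table on different footings.

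A reader might go further and infer that OLE adverse event rates are contaminated by vehicle-period events, or that the trial's best view of starting 0.46% is spoiled. The documents support neither. The adverse event definitions exclude vehicle-period onset, and the randomised, blinded comparison of 0.46% with vehicle is the cleaner view of the drug. The OLE has no concurrent control, so drift during it stays confounded with drug whichever baseline is used.

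**Conclusion.** The concern holds in a limited form. As written, the OLE laboratory and vital-sign summaries for former-vehicle subjects use a reference about 24 weeks before the first active dose, rising to 28 weeks or more for entry at Visit 11 or after a gap. Persisting vehicle-period laboratory abnormalities are counted as emergent in the OLE, some abnormalities that return on 0.46% are missed, and changes from baseline mix the two periods.

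The time distances follow directly from the visit schedule. The miscounts, 0.4 to 4 subjects per test in the illustration, rest wholly on assumed entry numbers and rates and should not be read as an estimate. The effect is on descriptive tables only; no primary or key secondary test depends on it. It is still worth correcting, because the SAP already accepts the principle for adverse events and efficacy, and the data needed are already collected.

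**What to change.** In SAP 3.3.6 and 5.3.4, define a second reference for OLE safety: the last non-missing value before the first open-label application, whether from Visit 10, Visit 11 or OLE Visit 1. Then:

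- Show laboratory and vital-sign changes in the OLE from both references, for all treatment groups, so that columns stay comparable. This follows SAP 5.2.9, which adds a Visit 10 reference for efficacy.
- Use the pre-OLE value to define OLE treatment-emergent laboratory abnormalities for subjects randomised to vehicle.
- Anchor the reference to the date of the first OLE application, not to the SAP's Day 1 (OLE). The SAP sets that date to Visit 10 for every entrant, whereas Protocol 5.5 dates the OLE start from OLE Visit 1. With the SAP date, an off-drug Visit 11 value would count as post-baseline for a subject entering there. The two documents should be reconciled on this.

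The cost is one definition, one derived flag and two references per table with footnotes. No assessment is added.

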#### Change from Baseline

Change from Baseline for a given endpoint is defined as the value at the analysis visit minus the baseline value.

#### Duration of alopecia

Date of Informed Consent minus the original onset date of alopecia as reported on the History of Alopecia page of eCRF.

#### Duration of current episode of patchy alopecia

Date of Informed Consent minus the onset date of current episode of Patchy Alopecia as reported on the History of Alopecia page of eCRF.

#### Prior Medications

Prior medications are those medications taken prior to the initiation of study medication, regardless of whether it continues into the blinded treatment period.

#### Concomitant Medications

Concomitant medications are those medications taken on or after the initiation of study medication. This definition includes medications started prior to the initiation of study medication but continuing concomitantly with the study medication.

#### DLQI Total Score - The scoring of each question is as follows:

Very much=scored 3, A lot=scored 2, A little= scored 1, Not at all= scored 0, Not relevant=scored 0, Question 7, 'prevented work or studying'=scored 3.

The DLQI is calculated by summing the score of each question resulting in a maximum of 30 and a minimum of 0. The higher the score, the more quality of life is impaired.

#### Adverse Event (AE)

An AE is any untoward medical occurrence in a subject administered a study medication(s) and which does not necessarily have a causal relationship with the study medication. An AE can therefore be any unfavorable and unintended sign or symptom associated with the use of a study medication (including an abnormal laboratory finding), whether related to the study medication. Thus, any new, clinically significant worsening of an existing sign, symptom or disease, should be considered an AE. Every new episode or clinically significant worsening of a chronic condition (*e.g.*, headaches, seasonal allergies, depression, or hypertension) should be reported as a separate AE, even if the condition is reported in the subject's medical history.

Treatment-Emergent Adverse Event (TEAE)

For the interim analysis of the DB treatment period, any recorded AE that occurs on or after the initiation of study medication and within 31 days after the date of Visit 10 or after the date of last DB dose of study medication will be considered treatment-emergent. For the OLE period analysis, an AE that occurs on or after the initiation of OLE study medication and within 31 days after the date of last dose of study medication will be considered treatment-emergent.

Treatment-emergent Laboratory Abnormalities

A treatment-emergent laboratory abnormality is defined as a result in which the baseline value is within normal laboratory limits and the post-baseline value is outside normal laboratory limits. If the relevant baseline assessment is missing, then any post-baseline value outside normal laboratory limits is treatment-emergent.

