5.5. Open-Label Extension

At Week 24 (Visit 10) or Week 28 (Visit 11), the subject may be given the option to move into the OLE treatment if the subject meets the OLE entry criteria in Section 5.5.1.

- If the subject declines the OLE, Visit 11 (Post-treatment) will be the last double-blind study visit.
- If the subject chooses to continue into the OLE, she/he must sign an OLE ICF/Accent, complete Visit 10 or Visit 11, as appropriate, and OLE Visit 1, prior to being dispensed open-label drug and receiving continued study medication application instructions. The subject will be scheduled for OLE Visit 2.
- If the subject enrolls in open-label treatment within 30 days of completion of Week 24 (Visit 10) or Week 28 (Visit 11), OLE Visit 1 will be conducted to obtain consent/assent and perform the procedures in the Schedule of Assessments. This will be considered the official date that the subject initiated OLE treatment.
- If the subject enrolls in open-label treatment > 30 days after completion of Week 28, OLE Visit 1 will be conducted in order to obtain consent/ assent, and complete the procedures detailed in the Scheduled of Events. This will be considered the official date that the subject initiated OLE treatment and the scheduling of subsequent visits will be based on this date.

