8.4.5. ECGs

Standard 12-lead ECGs will be performed by a qualified staff member at Screening (Visit 1), Baseline (Visit 2), Day 15 (Visit 4) and monthly visits during the double-blind period study and if subject is continuing in the OLE, at OLE Visit 6. The ECGs must be obtained using a standard 12-lead ECG with a 10mm/mV amplitude, at 25mm/sec and a 5 to 10-second duration. To ensure a steady heart rate the subject must rest quietly in the supine position for at least 5 minutes prior to performing the ECG.

A central lab, eResearch Technology, Inc. (ERT), will provide ECG equipment, supplies and site training. In addition, ERT will process ECGs received by the sites and report results via a secure study portal. The ECG results will be interpreted by a qualified health professional (evaluator) and the interpretation reported either directly on the tracing or in a separate report. The evaluator will interpret the results of every ECG and define the ECG as “normal” or “abnormal”. Variations such as minor ST changes (*i.e.*, <0.5mm depression) and early re-polarization are considered normal.

The investigator must review the evaluator’s interpretation of each subject’s screening ECG prior to Baseline (Visit 2). The investigator will review the evaluator’s interpretation of all ECG reports in a timely manner and comment on the clinical relevance of any result that is defined by the evaluator as abnormal.

Any abnormalities that are, in the opinion of the investigator, clinically significant, must be reported as history if found prior to the start of the first study medication application or as an AE if found after the start of the first study medication application (see Section 9.1.1).

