#### **Double-blind (DB) Period:**

A total of 120 subjects will be randomized in a 1:1:1 ratio:

- Vehicle Topical Solution BID for 24 weeks (6 months)
- ATI-50002 Topical Solution, 0.12%, BID for 24 weeks (6 months)
- ATI-50002 Topical Solution, 0.46%, BID for 24 weeks (6 months)

During the screening period, subjects will be assessed for eligibility into the study. Subjects will apply up to 4 mL of study medication to the entire scalp or patchy areas with a ½” margin twice a day for 24 weeks. Assessment of response to treatment will be performed at Week 4 (Visit 5), Week 8 (Visit 6), Week 12 (Visit 7), Week 16 (Visit 8), Week 20 (Visit 9), Week 24 (Visit 10), and post-treatment Week 28 (Visit 11). Safety and tolerability will be evaluated at each study visit by assessment of adverse events and vital signs, and at select visits, ECGs and clinical laboratory tests will be completed. The primary analysis will be conducted after all subjects complete Visit 10 or Visit 11 of the double-blind period.

Subjects who complete Visit 10 or Visit 11 (Week 24 or 28) will be eligible to enter a 28 week OLE. Subjects who decline or are not eligible for the OLE should be seen for the Visit 11 (Post-treatment) assessments.

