### **3.4. TIMING OF ANALYSES**

#### **3.4.1. Interim Analysis**

When all subjects have completed the blinded treatment period or terminated early from the blinded treatment period and data have been cleaned and forwarded for analysis, the study will be unblinded and the safety and efficacy analysis will be performed according to this SAP. See Section 8.1. for the list of proposed summary table and figures and data listings for the End of Double-Blind Treatment Period analysis.

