#### **4.2. SAFETY POPULATION**

The Safety population is defined as all randomized subjects who applied at least 1 application of study medication. Subjects in this population will be analyzed according to the treatment which they receive. All safety analyses will be based on this population.

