#### **5.2.9. Open-Label Extension**

For the open label extension period, efficacy will be evaluated based on the SALT, ALODEX, Scalp-ClinRO, Scalp-PRO, and SGITS. Descriptive summary statistics will be reported for the following:

- SALT score and change from baseline
- ALODEX Score and change from baseline
- Number (%) of subjects for each category of the Scalp-ClinRO (target patch and entire scalp)
- Number (%) of subjects for each category of the Scalp-PRO (target patch and entire scalp)
- Number (%) of subjects for each category of SGITS.

Summaries will include changes from baseline (study day 1) and changes from the end of the DB study (Visit 10). All by visit summaries will utilize the normal study visit based on CRF collection.

The efficacy summaries will be presented for the following subject groups based on the DB treatment assignments and the duration since end of DB period:

- Subjects who were randomized to Vehicle in the double-blind portion of the study
- Subjects who were randomized to ATI-50002 12% in the double-blind portion of the study who also entered the OLE less than 7 days from the end of their DB treatment period
- Subjects who were randomized to ATI-50002 12% in the double-blind portion of the study who also entered the OLE more than 7 days, but less than 60 days from the end of their DB treatment period
- Subjects who were randomized to ATI-50002 12% in the double-blind portion of the study who also entered the OLE at least 60 days from the end of their DB treatment period
- Subjects who were randomized to ATI-50002 46% in the double-blind portion of the study who also entered the OLE less than 7 days from the end of their DB treatment period

- Subjects who were randomized to ATI-50002 46% in the double-blind portion of the study who also entered the OLE more than 7 days, but less than 60 days from the end of their DB treatment period
- Subjects who were randomized to ATI-50002 46% in the double-blind portion of the study who also entered the OLE at least 60 days from the end of their DB treatment period.

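### The double-blind TEAE window does not close at the first open-label application, so AEs on open-label 0.46% can be tabulated under vehicle and 0.12%

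*SAP*

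**What the plan says.** The double-blind definition in SAP 3.3.6 starts at the first study medication and includes any recorded AE "within 31 days after the date of Visit 10 or after the date of last DB dose of study medication will be considered treatment-emergent". The sentence after it opens the extension window: it takes "an AE that occurs on or after the initiation of OLE study medication", up to 31 days after the last dose. Neither sentence mentions the other window.

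Early entry to the extension is a planned route. SAP 1.1 states: "Subjects who complete Visit 10 or Visit 11 (Week 24 or 28) will be eligible to enter a 28 week OLE". Protocol 5.5 requires the subject to "complete Visit 10 or Visit 11, as appropriate, and OLE Visit 1, prior to being dispensed open-label drug" and names no washout. SAP 5.2.9 plans efficacy summaries for active-arm subjects "who also entered the OLE less than 7 days from the end of their DB treatment period". Protocol 7.2 and SAP 1.1 give 0.46% to everyone in the extension, whatever their double-blind arm.

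Under SAP 3.4.1 the double-blind analysis is run "When all subjects have completed the blinded treatment period or terminated early from the blinded treatment period". On the Safety population, SAP 4.2 says: "Subjects in this population will be analyzed according to the treatment which they receive".

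**The concern.** The two windows overlap for anyone who starts the extension within 31 days of Visit 10. An AE that begins in the overlap meets both definitions. In the double-blind tables it appears under the subject's double-blind treatment, although it began on open-label 0.46%. For former 0.46% subjects the strength is unchanged and the overlap only adds follow-up. For former vehicle and 0.12% subjects the event is attributed to the wrong treatment.

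Safety compared with vehicle is part of the primary objective (Protocol 4.1, SAP 2). The definition feeds SAP Tables 14.3.1.1 to 14.3.1.7, which include serious, related and discontinuation TEAEs. With 40 subjects per arm, one misattributed subject moves a column by 1/40 = 2.5 points. The pooled display in SAP 5.3.4 counts only open-label AEs for vehicle subjects. The same event can therefore stand in the vehicle column of one report and count as active exposure in another.

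**Working it through.** The plan gives no figure of its own on this point to reproduce. The check is of the text, then of the overlap in days, then of what the overlap could do under assumed rates.

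**Does another rule remove the overlap?**
- SAP 4.2 assigns subjects to a treatment, not events.
- SAP 3.4.1 waits until the last subject has left the blinded period. Earlier entrants can have open-label AEs on record by then, and no per-subject data cut is stated.
- SAP 3.3.6 defines Period Day for each period but does not use it to limit TEAEs.
- SAP 5.3.1 excludes only AEs that start before study medication.
- The vehicle rule in SAP 5.3.4 applies to the pooled displays only.

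None of these closes the window.

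**Overlap.** Inputs: Visit 10 on Day 169 and Visit 11 on Day 197, each ±3 days (schedule of assessments), and the 31-day limit (SAP 3.3.6). The window ends on Day 169 + 31 = 200. Counted inclusively, overlap = max(0, 200 − first open-label day + 1) = max(0, 32 − gap from Visit 10).

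| Open-label start | Gap (days) | Overlap (days) |
|---|---|---|
| Visit 10, Day 169 | 0 | 32 |
| Day 176 | 7 | 25 |
| Visit 11, Day 197 | 28 | 4 |
| Visit 11, both visits at the edge of ±3 | 22 to 34 | 10 to 0 |
| Day 200 | 31 | 1 |
| Day 201 or later | 32 or more | 0 |

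The SAP does not say which anchor governs, Visit 10 or the last double-blind dose. If it is a last dose on Day 168, each non-zero count falls by one day.

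**Illustrations; every AE rate and entry share is an assumption.** Let p be the share of subjects entering at Visit 10, B the 24-week risk in the arm, and t the risk over the 32-day tail.
- Added follow-up = (1 − B) × p × t(own treatment).
- Contamination = (1 − B) × p × [t(0.46%) − t(own treatment)].

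The off-drug tail of subjects who do not enter is the same in every case and is left out.

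*Constant risk per 28 days: 1% vehicle, 3% on 0.12%, 5% on 0.46%.*
- 24-week risks: vehicle 1 − 0.99^6 = 5.85%; 0.12% 1 − 0.97^6 = 16.70%; 0.46% 1 − 0.95^6 = 26.49%. Difference 0.46% minus vehicle with the cut: 20.6 points.
- 32-day tails: 1 − 0.99^(32/28) = 1.14%, 1 − 0.97^(32/28) = 3.42%, 1 − 0.95^(32/28) = 5.69%.

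| Points | p = 20% | p = 50% | p = 80% |
|---|---|---|---|
| Vehicle, added follow-up | 0.2 | 0.5 | 0.9 |
| Vehicle, contamination | 0.9 | 2.1 | 3.4 |
| 0.46%, added follow-up | 0.8 | 2.1 | 3.3 |
| 0.12%, contamination | 0.4 | 0.9 | 1.5 |
| Difference as written | 20.4 | 20.1 | 19.7 |

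Vehicle contamination is 0.3 / 0.9 / 1.4 subjects of 40. The difference barely moves because the extra days raise the 0.46% column by nearly as much as the vehicle column.

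*Front-loaded reaction: 3% vehicle, 9% on 0.12% and 15% on 0.46% in the first 28 days, then 1% per 28 days.*
- 24-week risks: vehicle 1 − 0.97 × 0.99^5 = 7.75%; 0.12% 1 − 0.91 × 0.99^5 = 13.46%; 0.46% 1 − 0.85 × 0.99^5 = 19.17%. Difference with the cut: 11.4 points.
- Background tail: 1.14%. Tail on first exposure to 0.46%, full reaction: 1 − 0.85 × 0.99^(4/28) = 15.12%.
- Former vehicle subjects have already used the solution for 24 weeks. If the 3% vehicle component does not recur, their tail is 1 − (0.85/0.97) × 0.99^(32/28) = 13.37%.

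| Points | p = 20% | p = 50% | p = 80% |
|---|---|---|---|
| Vehicle, added follow-up | 0.2 | 0.5 | 0.8 |
| Vehicle, contamination (full reaction) | 2.6 | 6.4 | 10.3 |
| Vehicle, contamination (vehicle part removed) | 2.3 | 5.6 | 9.0 |
| Difference as written (full reaction) | 8.8 | 4.9 | 1.0 |
| Difference as written (vehicle part removed) | 9.1 | 5.7 | 2.3 |

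The full-reaction contamination of vehicle is 1.0 / 2.6 / 4.1 subjects. Without contamination the difference would stay at 11.4 / 11.3 / 11.3. The 0.12% column gains between 0 (no new reaction on moving to 0.46%) and 2.4 / 6.0 / 9.7 points (full reaction).

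**The case against.** The best defence is that this is an unstated boundary, not a decision to misattribute. The definition is scoped to the double-blind analysis, the SAP separates the periods elsewhere, and SAP 3.4.1 does not say that open-label AE records will be in the data transferred for that analysis. That inclusion is indeed an inference. But the rule covers any recorded AE in the window, and no sentence keeps open-label records out. A programmer following it would include them.

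The second line is size. No rate or entry share comes from the documents. The extension was added by Amendment 7, entry at Visit 11 is equally allowed, and the SAP plans groups with gaps beyond 7 days and of at least 60 days. High same-day entry cannot be presumed. With the constant rates above, a 4-day overlap at Visit 11 contaminates vehicle by only 0.1 / 0.3 / 0.4 points. All of this stands. So does the point that a vehicle reaction need not recur on switching, which is why the front-loaded case is shown both ways.

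Third, the AE tables are descriptive (Protocol 11.5, SAP 5.3.1), no test or efficacy result uses them, and AEs and study drug administration are listed by subject. A reader could partly re-derive the split. That limits the harm but does not correct the tabulated comparison.

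**Conclusion.** The definition is wrong as written and should be fixed. For a subject who enters at Visit 10, up to 32 days on open-label 0.46% count as double-blind time, and AEs starting then are counted in both sets of tables. This follows from the text and needs no assumption about rates.

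The effect on the reported comparison is unknown. It is under 1 point in the constant-risk case. A large dilution, such as 11.4 points down to between 1.0 and 2.3, needs both a reaction concentrated in the first weeks of exposure and high same-day entry; the documents establish neither. Efficacy conclusions are untouched.

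**What to change.** In SAP 3.3.6, end the double-blind TEAE window at the earlier of its 31-day limit and the first open-label application, and assign AEs with onset after that application to the extension only. The overlap is then zero for every subject. Use the actual first application date: the SAP sets Day 1 (OLE) at Visit 10 for every entrant, which would cut too early for those who start later.

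Add a rule for same-day rollover. Classify by recorded onset relative to the first open-label application. Keep findings from Visit 10 assessments in the double-blind period, because that visit is completed before open-label drug is dispensed, and a clinically significant abnormality is reported "as an AE if found after the start of the first study medication application" (Protocol 8.4.5 for ECGs; 8.4.1 and 8.4.3 are to the same effect for vital signs and laboratory results). The documents do not show that AE onset time is captured, so flag in the listing any date-only AE whose order is unclear. Report by arm how many subjects started the extension inside the window.

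The cost is one sentence, one derivation and one same-day rule. Subjects who roll over contribute less post-treatment follow-up to the double-blind tables. That cannot be avoided, because they are already on open-label drug.
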